9.4.2. Handling of Missing Data for Select Endpoints

Assessment of number of treatable lesions is planned for the baseline visit, the EOS visit and each visit where treatment is applied. Endpoints that are based on these assessments include percent reduction from baseline of treatable lesions, change from baseline in treatable lesions and proportion of subjects exhibiting 90% or greater reduction of treatable lesions from baseline. If the EOS assessment of number of treatable lesions is not available, the number of treatable lesions will be imputed from earlier assessments of lesions count using last observation carried forward (LOCF). The LOCF method uses

information from the last available assessment of the measurement to include subjects with missing data in analysis. Similarly, LOCF will be used to impute other post baseline visit where lesion count is not available. One exception is if only the baseline lesion count is available for a subject. In that instance, the baseline value will not be carried forward and the number of treatable lesions will be left as missing.

Missing composite CDLQI scores at the EOS visit will be handled using the same method of LOCF as described above for imputing missing lesion counts. For handling individual questions with missing responses, see Section 10.4 for more details.

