Parents or guardians must provide informed consent, and pediatric subjects older than 5 years must provide assent as required by the IRB before any study procedures are conducted. Subjects must meet all study eligibility criteria through a complete review of pertinent medical history, a symptom/sign evaluation, and limited physical examination.

4. Determination of Sample Size

The primary objective of the study is to determine the presence or absence of systemic cantharidin exposure from application of VP-102. Thus, power calculations were not performed. There will be up to 40 subjects enrolled with the goal of 16 completing all blood draws in the Exposure group. Any subject in the Exposure group who does not

complete all blood draws may continue to receive treatment, but will be replaced. At least 3 subjects in the Exposure group will be from 2-5 years of age.

5. Statistical Methods

The statistical analyses will be reported using summary tables, figures and listings (TFLs). Numbering for TFLs will be based on the recommended numbering convention provided by the International Conference on Harmonization. Continuous variables will be summarized with means, standard deviations, medians, minimums and maximums.

Categorical variables will be summarized by counts and percent of subjects in corresponding categories. Where appropriate, 95% confidence intervals will be included. Missing values are not considered for percent calculations, unless stated otherwise. In those cases, footnotes will specify the percent basis. All summary tables will present a summary of the Exposure treatment group and Standard treatment group. In addition, an overall/total summary will be provided that will include subjects who were replaced.

Individual subject data obtained via the electronic data capture (EDC) system and from external vendors will be presented in listings.

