7.3. Demographic and Baseline Characteristics

Demographics variables will include: age, sex, ethnicity and race. Age will be calculated by comparing date of birth to date of informed consent.

Baseline characteristics will include: medical history, molluscum history, height, weight and body mass index (BMI). BMI will be calculated by weight (kg) / height (m^2). Molluscum history variables that will be summarized include time since clinical diagnosis (as compared to informed consent), age at diagnosis and any previous treatments for molluscum lesions. Medical history will not be summarized in a table, but will be displayed in a listing.

Continuous variables will be summarized using descriptive statistics. Categorical variables will be summarized using counts and percentages. Demographics, baseline characteristics and molluscum history will be summarized for all 3 analysis populations (ITT, Safety, Exposure).

8. Exposure Analysis

Plasma samples from the Exposure group will be analyzed at each time point using a GC/MS assay method that was previously validated by Pacific Bio Labs (Study number 14I0376R-A03). Samples will be listed as either below or above the LLOQ (1 ng/ml).

An overall and by time point summaries of concentration results above and below the LLOQ will be provided using the Exposure population. Concentration levels above LLOQ will be considered evidence of the presence of systemic cantharidin (primary objective). A listing will be generated which will show results of LLOQ as well as any results reported above LLOQ.

9. Efficacy Analysis

The ITT and Exposure population will be used for efficacy analysis. Results will be summarized using descriptive statistics and counts/percentages. Where appropriate, 95% confidence intervals may be generated as well.

For the purposes of the analyses, all lesions reported in the study will be considered treatable. Although the protocol specifies study objectives and efficacy variables in terms of treated lesions, actual analysis will be carried out on treatable lesions. The reason to carry out analysis on treatable lesions is to avoid any bias or confusion with determining whether a lesion was treated. This is also in alignment with other studies in this clinical program per regulatory feedback. As a result, considering treatable lesions instead of treated lesions will be a more conservative approach when analyzing study results.

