9.4. Handling of Dropouts or Missing Data

All subjects who receive treatment will be evaluated in the ITT population. Subjects who do not complete all of the scheduled blood draws will be replaced. In the event a subject requests to be removed from the study due to study related adverse events or additional spreading of disease, data will be collected and analyzed as a treatment failure and not replaced.

Unless described otherwise in subsequent sections, analyses will be carried out with the data available using no imputation for missing data. A description of how missing data will be handled for the primary endpoint and secondary endpoints is included below.

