9.4.1. Handling of Missing Data for Complete Clearance Endpoint

The efficacy endpoint, proportion of subjects exhibiting complete clearance of all treatable lesions, is to be assessed a maximum of four times during the study. Assessments are to be done at Day 21, Day 42, Day 63 and Day 84 (EOS).

Subjects who do not have an assessment of complete clearance of all treatable lesions at any of the scheduled assessments will be considered to have missing data for this endpoint. Since the endpoint is complete clearance on or before Week 12, a subject will be considered to have met the condition of complete clearance if that subject has at least one assessment of complete clearance, regardless of what other assessments of clearance may be missing. If a subject has only non-missing assessments of not achieving clearance, then that subject will not be considered to have cleared. If a subject is missing all assessments of clearance, then that subject will be considered to have not cleared.

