10.1. Complete Clearance of Treatable Lesions

Counts and percent of subjects who have complete clearance of all treatable molluscum lesions on or before EOS will be displayed by treatment group. Complete clearance will be defined as no lesions (lesion count=0) reported for a subject per the Skin Examination form. Summaries of complete clearance will also be provided by visit. Note: all lesions reported on the Skin Examination form will be considered treatable. Number of inflamed lesions, number of lesions not treated and reasons why lesions were not treated will be displayed in listings.

The EOS visit is scheduled to occur on Day 84 and 21 days (+/- 4 days) after their last treatment visit. For the analyses of this endpoint, only visits that occur prior to Day 100 will be considered for determining complete clearance. Subjects without an assessment of lesion count within this visit window will be counted as not cleared.

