10.2. Lesion Percent (%) Reduction at EOS

At the EOS visit, the number of lesions will be reported. The percent change in number of lesions will be calculated as described in Section 10.3. Based on the percent reduction of lesions at EOS, subjects will be assessed and assigned to one of 2 categories: $\geq 90\%$ reduction of lesions, $<90\%$ reduction in lesions. Subject counts and percentage of subject for each of these categories will be displayed by treatment group over the entire study and by visit.

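### Treated subjects with only a baseline lesion count drop out of the ≥90% reduction denominator but stay in the complete clearance denominator as not cleared

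*SAP*

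**What the plan says.** Protocol 2.3 lists the proportion of subjects with a 90% or greater lesion reduction at EOS as an exploratory endpoint, and Protocol 7.2.4 assigns it to the ITT population. SAP 9.4 confirms the set: "All subjects who receive treatment will be evaluated in the ITT population". SAP Section 9 adds a second set: "The ITT and Exposure population will be used for efficacy analysis".

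SAP 9.4.2 names the ≥90% endpoint among those it governs. A missing EOS count is filled by LOCF, with one exception. If the subject has only a baseline count, "the baseline value will not be carried forward and the number of treatable lesions will be left as missing". The general rule in SAP Section 5 is: "Missing values are not considered for percent calculations, unless stated otherwise". SAP 10.2 describes the table: "Based on the percent reduction of lesions at EOS, subjects will be assessed and assigned to one of 2 categories", namely ≥90% and <90%. The counts and percentages "for each of these categories will be displayed by treatment group over the entire study and by visit". It has no category or rule for a subject without a percent reduction.

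For complete clearance the SAP does give a rule. Section 9.4.1 says: "If a subject is missing all assessments of clearance, then that subject will be considered to have not cleared". Section 10.1 repeats the principle for its visit window: "Subjects without an assessment of lesion count within this visit window will be counted as not cleared".

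SAP 9.4 and Protocol 2.4 also say that a subject who asks to leave because of study-related adverse events or spreading disease is analysed as a treatment failure. Neither says what that means for each endpoint.

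**The concern.** Two responder rates built on the same lesion counts treat the same unassessed subject differently. One counts the subject as a failure and the other removes the subject. Complete clearance is a 100% reduction, so readers will naturally set the two rates side by side, yet part of any difference between them may come from the denominator alone. Subjects who are treated on Day 1 and never counted again are also the least likely to be missing at random, and dropping them moves the rate in one direction only.

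The Exposure population table has the same weakness. SAP Section 6 admits a subject to that population on the Day 1 blood draws alone, so a subject can belong to it without any post-baseline lesion count.

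A narrower question concerns the treatment-failure rule. SAP 9.4.2 and 10.2 do not say that failure means <90% reduction. Read literally, a subject who withdraws for adverse events or spread could be classified by a carried-forward count or, if only baseline exists, dropped. SAP 9.4 can also be read as already governing these subjects. On that reading the denominator problem is confined to baseline-only subjects lost for other reasons, such as loss to follow-up or noncompliance.

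**Working it through.** The plan states no response rate, dropout rate or sample size derivation for this endpoint, so there is no figure to reproduce. The check has two parts.

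**Following one subject through the rules.** Take an ITT subject treated on Day 1 with no later lesion count, lost for a reason other than adverse events or spread.

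| Step | ≥90% reduction | Complete clearance |
|---|---|---|
| Imputation | None; left missing (SAP 9.4.2) | Not cleared (SAP 9.4.1, 10.1) |
| Percentage basis | Missing excluded (SAP 5); no override in SAP 10.2 | Override stated; subject retained |
| Result | Leaves the denominator | Stays in as a failure |

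**Size of the difference.** Let N be the number of ITT subjects, k the number with baseline only, and r the number of responders. The current wording reports r/(N − k). Counting the k subjects as <90% gives r/N. The gap is

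r/(N − k) − r/N = (r/N) × k/(N − k),

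which is zero when k = 0 and never negative.

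Inputs from the documents: N = 16 (the cap on the standard group and the target for exposure completers), N = 32 (16 + 16), and N = 40 (maximum enrolment). Assumed inputs: r/N of 25%, 50% or 75%; k of 1 to 2 in a group of 16, and 1 to 4 overall.

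| N | k | r/N = 25% | r/N = 50% | r/N = 75% |
|---|---|---|---|---|
| 16 | 1 | 4/15 = 26.7% (+1.7) | 8/15 = 53.3% (+3.3) | 12/15 = 80.0% (+5.0) |
| 16 | 2 | 4/14 = 28.6% (+3.6) | 8/14 = 57.1% (+7.1) | 12/14 = 85.7% (+10.7) |
| 32 | 1 | 8/31 = 25.8% (+0.8) | 16/31 = 51.6% (+1.6) | 24/31 = 77.4% (+2.4) |
| 32 | 4 | 8/28 = 28.6% (+3.6) | 16/28 = 57.1% (+7.1) | 24/28 = 85.7% (+10.7) |
| 40 | 1 | 10/39 = 25.6% (+0.6) | 20/39 = 51.3% (+1.3) | 30/39 = 76.9% (+1.9) |
| 40 | 4 | 10/36 = 27.8% (+2.8) | 20/36 = 55.6% (+5.6) | 30/36 = 83.3% (+8.3) |

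Figures in brackets are percentage points. For scale, with N = 16, k = 2 and r = 12, the Clopper-Pearson 95% interval is 57.2% to 98.2% for 12/14 and 47.6% to 92.7% for 12/16. The shift is small against the imprecision of so small a group.

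An extreme case shows the denominator effect in isolation. If 12 of 16 subjects clear and the other 4 have baseline only, clearance is 12/16 = 75.0% while ≥90% reduction is 12/12 = 100%.

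**The case against.** The strongest reply is that this is a disclosed choice. SAP 9.4.2 names the endpoint and states the exception openly, and Protocol 7.2.7 leaves missing data to the SAP. Belonging to the ITT population does not promise every member an imputed value. Declining to carry a baseline value forward is sensible for change and percent change. Counting every unassessed subject as a non-responder is itself a convention and may understate response.

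The plan is also transparent. SAP Section 5 calls for footnotes where a percentage departs from the default basis, SAP 7.1 tabulates discontinuations with reasons, and counts accompany percentages, so a reader could recompute r/N.

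Few subjects can be affected, because any one later count brings LOCF into play and Protocol 2.3.1 and 6.1 ask sites to seek EOS assessments from those who leave early. The two rates also differ by design: clearance counts at any time up to EOS with a Day 100 cut-off, whereas the ≥90% endpoint is taken at EOS with LOCF and no stated cut-off.

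Most of this stands and limits the importance of the point. It does not remove it. A responder proportion needs its own rule for unassessed subjects, the SAP supplies one for clearance, and it gives no reason for the opposite treatment here. The timing differences between the endpoints do not justify different denominators.

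**Conclusion.** The point holds and is minor. For baseline-only subjects lost for reasons outside the treatment-failure rule, the wording clearly removes them from the ≥90% denominator while clearance retains them. For those who withdraw because of study-related adverse events or spread, the SAP is ambiguous rather than plainly wrong.

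The gaps tabulated above measure the distance between two conventions, not bias against a true rate. They depend on an assumed number of baseline-only subjects and assumed response rates; the upper end needs 12.5% of treated subjects (2 of 16, or 4 of 32) never to return for a count, together with 75% response. The endpoint carries no formal comparison, and neither the plasma exposure result nor the complete clearance result is affected.

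**What to change.** In SAP 9.4.2 and 10.2, state that for the ≥90% endpoint ITT subjects with no post-baseline count, and subjects who are treatment failures under SAP 9.4, are counted as <90% reduction over the full ITT denominator. Apply the same denominator rule to the Exposure population table. Leave change and percent change as they are, with baseline-only subjects missing. Keep the present LOCF, observed-denominator version as a sensitivity analysis, since the non-responder convention could understate response.

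The cost is one or two sentences of SAP text and one extra table. The reported exploratory rate may be slightly lower.

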9.5. Interim Analysis and Data Monitoring

No formal interim analysis or data monitoring is planned for this study.

9.6. Multiple Comparison/Multiplicity

No formal statistical comparisons are planned; thus, no adjustment for multiple comparisons is needed.

9.7. Examination of Subgroups

Analyses based on subgroups of interest may be carried out for exploratory purposes. Possible analyses include the following:

- Baseline Lesion Count: 1-20 lesions, 21-40 lesions, 41 or more lesions. Note: lesion count categories may be adjusted based on distribution of baseline lesion counts.
- Age: 2-5 years old, 6-11 years old, 12 years or older.
- Gender: Female, Male.
- Subjects 12 or older with genital lesions being 50% or greater percent of lesions at baseline. A separate analysis will be run for those subjects who do not qualify for this subgroup.
- Presence or absence of atopic dermatitis.

10. Methods of Efficacy Analysis

10.1. Complete Clearance of Treatable Lesions

Counts and percent of subjects who have complete clearance of all treatable molluscum lesions on or before EOS will be displayed by treatment group. Complete clearance will be defined as no lesions (lesion count=0) reported for a subject per the Skin Examination form. Summaries of complete clearance will also be provided by visit. Note: all lesions reported on the Skin Examination form will be considered treatable. Number of inflamed lesions, number of lesions not treated and reasons why lesions were not treated will be displayed in listings.

The EOS visit is scheduled to occur on Day 84 and 21 days (+/- 4 days) after their last treatment visit. For the analyses of this endpoint, only visits that occur prior to Day 100 will be considered for determining complete clearance. Subjects without an assessment of lesion count within this visit window will be counted as not cleared.

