Test product, dose, and mode of administration: Study drug (VP-102) is contained within a single-use applicator. Topical administration results in approximately 5 to 10 μ L of Study drug per molluscum lesion (approximately 1mm to 4mm in diameter). The VP-102 single-use applicator contains 450 μ l (3.15 mg) of 0.7% w/v cantharidin. Up to 2 applicators may be used per patient, but a second applicator may only be necessary if treating >50 lesions.

STUDY SYNOPSIS (continued)

Name of sponsor company: Verrica Pharmaceuticals, Inc.
Name of finished product: VP-102 (0.7% w/v cantharidin delivered via a single-use applicator)
Name(s) of active ingredient(s): Cantharidin
Duration of treatment: The length of study participation from treatment Day 1 is up to approximately 84 days (12 weeks): Up to 4 applications of Study drug at approximately 21-day intervals, followed by a EOS visit approximately 21-days after the final treatment. Subjects are instructed to gently wash all treated lesions with soap and warm water the morning following application (24 hours after treatment or earlier if significant pain or significant blistering has occurred). If not inconvenient, the patient will target a 24-hour removal time point. Washing of intact blisters should be gentle and without use of a washcloth. Washing in a bath or shower is encouraged.
Criteria for evaluation The primary objective of the exposure protocol group is to determine the presence or absence of systemic cantharidin. Due to sample size, power calculations will not be performed. Data will be summarized using descriptive statistics (sample size, mean, median, standard deviation, minimum, maximum) for continuous variables and frequencies and percentages for discrete variables. Corresponding by-subject data listings will be tabulated.
Efficacy: All subjects who meet the screening eligibility criteria for the study and enrolled in the study, will be evaluated for efficacy. Clinical response to treatment of molluscum lesions will be evaluated at each scheduled visit until EOS by counting all molluscum lesions. New or additional treated and untreated lesions will also be counted. LSR will be assessed at each study visit and the EOS visit by the Investigator or trained personnel with a protocol specific LSR form.

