- a. Screening can occur up to 14 days prior to Study drug application on Day 1. Screening can occur on the same day as treatment Day 1/Study drug application. An IRB-approved ICF must be signed before any study specific procedures are performed.
- b. Subjects may be scheduled 21+/- 4 days after treatment in the event of scheduling conflict. If possible the next treatment or study visit should be scheduled 21 days from the day of the subject's last study visit. The 24 hour follow-up may be conducted at +/- 3 hours. Study medication should be removed after the 24 hour draw is completed.
- c. At end of the study (EOS, ~Day 84), all subjects with unresolved molluscum lesions or unresolved treatment-emergent AEs, will be treated by the investigator per local standard of care. Patients who clear all lesions at study visits prior to ~Day 84 will complete all study related assessments that were required at the EOS visit and will not need to return for further assessment. A study completion form will be completed on the day they are cleared.
- d. Confirmation of eligibility criteria.
- e. Demographics: date of birth, sex, race/ethnicity will be collected.
- f. Vital signs (e.g., temperature & heart rate) will be obtained at screening and at each treatment prior to application of Study drug.
- g. Limited physical examination. Symptom- or AE-directed physical examination may be performed if warranted. (See Source/CRF for further outline of assessment.)
- h. Regional lesion counts (head/neck, trunk, upper/lower extremities) should be performed.
- i. LSR assessment will be performed by the Investigator or trained personnel with a protocol-specific LSR form at each treatment visit and the EOS visit.
- j. CDLQI assessment to be completed prior to Study drug application and at EOS visit. CDLQI must be repeated if the first treatment is not completed within 7 days.
- k. To be performed prior to Study drug application and at EOS in any females of childbearing potential (females that are capable of menstruating).

- l. Photography of molluscum lesions will occur at selected clinical sites only.
- m. Study drug may be gently removed from individual lesions prior to 16 hours of application in the event of significant blistering, significant pain or treatment emergent AEs. Study drug should not be removed from the remaining unproblematic lesions until the 24 hour time point is reached. Every effort should be made to complete the PERIT at 24 hours after application.

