Molluscum lesions will be treated without occlusion in all anatomic areas including the face, trunk, back, arms, legs, hands, feet, genital region and buttocks as long as the physician feels it is safe to do so.

The study duration from Day 1 through the EOS visit is up to 12 weeks. Pre-study screening for eligibility (informed consent, inclusion/exclusion criteria and medical history) will occur up to 14 days before, or on Day 1/Study drug administration. Subjects will be treated with application to molluscum lesions every 21 days (\pm 4 days) for a maximum of 4 treatment sessions. Subjects that completely clear prior to ~Day 84 will

complete their EOS visit on that day. In the event of scheduling conflicts in subsequent visits after the Day 1 treatment, subjects may be scheduled on 21 ± 4 days following their previous treatment. The next study visit should then be scheduled 21 days after the previous treatment.

Assessment of local skin reactions (LSR) will be performed by the investigator or trained member of the research team at each treatment visit and the EOS visit. LSRs will be recorded as adverse events. LSRs will include the following adverse events: blistering, pain, pruritus, erythema, edema, erosion/ulcerations, flaking/scaling/dryness, scabbing/crusting and pigmentation changes. A Skin Quality Assessment will also be performed as part of the review of LSRs and will assess erythema, flaking/scaling/dryness, scabbing/crusting, hyperpigmentation, hypopigmentation and scarring, if applicable.

Parent/subject quality of life and measure of impact of skin disease will be assessed with the CDLQI prior to application of Study drug at each treatment session and at the EOS visit. Subjects will also complete a Safety Monitoring Questionnaire at Visits 2-5.

Subjects will be given a 24-hour phone number to call the investigator or a clinical research team member in the event of questions or AEs. Evaluations will also be provided by the subject or parent/guardian using the Patient Evaluation of Response to Investigational Treatment (PERIT) form the following day after Study drug application. Parents will also be asked to take and send photos via text or e-mail to the study team for assessment during the 24-hour follow-up call. All observed AEs, local skin reactions and parent-reported AEs will be recorded.

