9.1. Efficacy Variables

Efficacy endpoints to be analyzed are:

- Proportion of subjects exhibiting complete clearance of all treated molluscum lesions (baseline and new) on or before Week 12 (EOS).
- Proportion of subjects exhibiting a 90% or greater reduction of all molluscum lesions (baseline and new) at the EOS visit.
- Percent reduction of molluscum lesions from baseline at the EOS visit.
- Change from baseline in the number of molluscum lesions at the EOS visit.
- Change from baseline in the quality of life and impact of skin disease as measured by the Children's Dermatology Life Quality Index (CDLQI) assessment at the EOS visit.
- Subject reported spread to siblings as measured by any new occurrence of molluscum in siblings of subject.

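### The Day 100 cut for complete clearance in SAP 10.1 stops one or two days short of the latest end-of-study visit that the ±4-day windows allow

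*SAP*

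**What the plan says.** **The cut.** For the complete-clearance endpoint, SAP Section 10.1 says "only visits that occur prior to Day 100 will be considered for determining complete clearance". It adds: "Subjects without an assessment of lesion count within this visit window will be counted as not cleared". The endpoint, as listed in SAP Section 9.1, is "complete clearance of all treated molluscum lesions (baseline and new) on or before Week 12 (EOS". It is the only secondary endpoint in Protocol Section 2.3.

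**The visit windows.** SAP Section 3 (Study Design) says that "subjects may be scheduled on 21 ± 4 days following their previous treatment", and Protocol Section 2.1 has the same rule. Footnote b to the protocol's schedule of assessments reads: "Subjects may be scheduled 21+/- 4 days after treatment in the event of scheduling conflict", and then "If possible the next treatment or study visit should be scheduled 21 days from the day of the subject's last study visit". SAP 10.1 itself says: "The EOS visit is scheduled to occur on Day 84 and 21 days (+/- 4 days) after their last treatment visit". The number of intervals comes from the protocol synopsis (Duration of treatment): "Up to 4 applications of Study drug at approximately 21-day intervals, followed by a EOS visit approximately 21-days after the final treatment".

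**The neighbouring rules.** SAP 9.4.1 treats a subject as cleared if any one assessment shows clearance, and as not cleared if all available assessments show lesions. It sets no day limit. SAP 10.2 and 10.3 take the ≥90% reduction and the percent change from the EOS count, also with no day limit.

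**The concern.** The ±4 days are counted from the previous treatment, and nothing requires a delayed subject to return to the Day 1 calendar. Lateness can therefore build up over four intervals. If the cut is earlier than the latest visit those windows allow, a subject who kept to the protocol throughout can have a genuine clearance ignored.

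Two things are at stake. The error can only turn a clearance into a failure, and it does so on the sole secondary endpoint. The SAP would also classify one subject in two ways: a 100% reduction in one table and not cleared in another, with 9.4.1 and 10.1 giving the programmer different answers.

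**Working it through.** **Inputs**

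- Intervals: 4 (treatments 1–2, 2–3, 3–4, and 4–EOS), from the protocol synopsis.
- Allowed interval: 21 ± 4, so 17 to 25 days, from Protocol 2.1 and SAP Section 3.
- Cut: visit day strictly below 100, from SAP 10.1.
- Subjects: 32, being the 16 planned exposure completers plus at most 16 in the standard group; at most 40 enrolled (Protocol 2.2).

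**Step 1: the plan's nominal day.** 4 × 21 = 84, which matches the stated EOS day.

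**Step 2: the latest compliant visits.** At 25 days per interval, the four visits fall 25, 50, 75 and 100 days after first treatment. If first treatment is numbered Day 1, they are Days 26, 51, 76 and 101. The SAP does not say which numbering the cut uses. The labels 21/42/63/84 fit elapsed days, since exact 21-day spacing from Day 1 would give 22/43/64/85; yet the first treatment visit is labelled Day 1. The latest compliant EOS is Day 100 or Day 101, and both fail the rule. Since 84 + 4 × 4 = 100, the cut looks like a strict inequality where an inclusive one was meant, but the documents do not explain the choice.

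**Step 3: classification of one subject.** Take a subject with baseline count B > 0, lesions at treatments 2 to 4, and a count of 0 at that EOS.

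- SAP 10.1 ignores the EOS visit. The remaining assessments all show lesions, so the subject is not cleared.
- SAP 9.4.1, read on its own, finds one assessment of clearance, so the subject is cleared.
- SAP 10.2 and 10.3: (0 − B)/B × 100 = −100%, so the subject is in the ≥90% category.

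**Step 4: how many schedules are affected.** Two sets of whole-day offsets were enumerated for the four intervals: −4 to +4 (9⁴ = 6561 combinations) and 0 to +4 (5⁴ = 625). On elapsed days, exclusion needs all 16 slip days: 1 combination. With first treatment as Day 1, it needs 15 or 16 slip days: 4 + 1 = 5 combinations.

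| Offsets | Elapsed days | First treatment = Day 1 |
|---|---|---|
| −4 to +4 | 1/6561 = 0.015% | 5/6561 = 0.08% |
| 0 to +4 only | 1/625 = 0.16% | 5/625 = 0.8% |

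**Step 5: chance that any of 32 subjects is affected**, 1 − (1 − p)³²:

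- Offsets −4 to +4: about 0.5% to 2.4%.
- Late shifts only: about 5% to 23%.

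These treat combinations as equally likely, subjects as independent, and all 32 subjects as reaching EOS after four treatments. They count late EOS visits. Misclassification also requires that the subject first clears at that visit, so under either offset model they are upper bounds.

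**Step 6: weight of one subject.** 100/16 = 6.25 percentage points; 100/40 = 2.5 points.

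**The case against.** **The window could mean Day 84 ± 4.** The latest EOS would then be Day 88 and nothing compliant would be lost. The text does not support this: SAP 10.1 attaches the ±4 days to the last treatment visit, and Protocol 2.1 and SAP Section 3 attach them to the previous treatment.

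**The scenario is remote.** This stands. The windows are for scheduling conflicts and the default spacing is 21 days, so equal weights probably overstate the risk. A subject must be late by essentially the full allowance four times and first clear at EOS. Anyone clear earlier leaves the study then and counts as cleared. The study is descriptive, with no power calculation and no formal comparison, so no test depends on the result.

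**A time-bounded endpoint may have a cut that the others lack.** This also stands. Clearance is defined up to a time point, while the ≥90% and change endpoints are defined at the EOS visit. A cut on clearance alone is not an error; the error is that it falls inside the compliant window.

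**Stronger readings that the documents do not support**

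- A reader might take Day 101 as settled. It depends on a day numbering that the SAP does not state.
- A reader might take 23% as the chance of a wrong result. It is the largest of four upper bounds and concerns only a late visit.
- A reader might take the SAP 10.1 sentence on subjects without an assessment in the window as the rule that fails this subject. It is not: the subject has in-window counts from treatments 2 to 4, and the failure comes from ignoring the EOS visit.
- A reader might object that clearance is accepted up to Day 99, 98 days or 14 weeks after Day 1, under a Week 12 label. Week 12 is tied to EOS as a nominal visit name, so a new label is optional.

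**Conclusion.** The mismatch is real under either day numbering: SAP 10.1 can exclude an EOS visit that the plan's own windows allow, and SAP 9.4.1, 10.2 and 10.3 then disagree with it about the same subject. It loses one day on elapsed-day numbering and two if first treatment is Day 1.

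The practical effect is very small, and an affected subject in an actual dataset is unlikely. The frequencies rest on the assumed offset distributions, since the documents give no data on visit timing. The conclusion that a compliant visit can be excluded does not depend on those distributions. This is a minor correction, and it gives no reason to distrust the clearance endpoint as a whole.

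**What to change.** - **SAP 10.1:** state how days are numbered, and replace the cut with one that includes the last compliant day: through 100 days after first treatment, which is Day 101 if first treatment is Day 1. Writing only through Day 100, with first treatment as Day 1, would still exclude one combination.
- **SAP 9.4.1:** cross-refer to the same limit, so that both sections give one classification.
- **SAP 10.2 and 10.3:** do not add the cut. An EOS count after the limit might then be treated as unavailable, and SAP 9.4.2 would replace an observed count by last observation carried forward. Instead, footnote any subject whose clearance and percent-reduction classifications differ because of the window.

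The cost is one revised sentence, one cross-reference and a table footnote. No new data or protocol change is needed. It should be settled before database lock, because SAP Section 5 treats analyses added afterwards as post hoc.
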